Document Date: June 23, 2022

Three Dimensional Assessment of Maxillary Molars Following Distalization Using Two Different Approaches

A Thesis
Submitted to Faculty of Dentistry
Ain-Shams University
In Partial Fulfillment of the Requirements of
Master's Degree in Orthodontics

Faculty of Dentistry
Ain Shams University
2022

Statistical analysis

Statistical analysis was performed with SPSS 20^{®*}, Graph Pad Prism^{®**}, and Microsoft Excel 2016^{***}.

All quantitative data were explored for normality by using Shapiro Wilk Normality test and presented as means and standard deviation (SD) values. All qualitative data were presented as frequency & percentage. All data were presented in (43) tables & (38) graphs.

Tests used:

- Comparisons 2 different groups was performed by using Mann Whitney test.
- Comparisons 2 successive follow ups periods was performed by using Paired t-test.
- Comparison between quantitative continuous data (Age & Duration) was performed by Independent t-test.
- Comparison between qualitative dichotomous data (Gender) was performed by Chi square test.
- Reliability test was performed by using Intra-class Correlation Coefficient (ICC).

* Statistical Package for Social Science, IBM, Armonk, NY, USA.

** Graph Pad Technologies, San Diego, CA, USA

*** Microsoft Co-operation, Redmond, WA, USA.

* All results presented as:

I. Normality test.

II. Baseline characteristics:

- A. Age.
- B. Gender.
- C. Duration
- D. Pretreatment measurements. (Appendix IV).

III. Measurements

The following measurements were carried for both group I and group II as well as in comparison between the two groups.

A. Skeletal measurements

- 1. Skeletal antero-posterior measurements.
- 2. Skeletal vertical measurements.

B. Dental measurements

- 1. Angular
- 2. Linear

C. Soft tissue measurements.

IV. Reliability: (Appendix V)

- A. Inter-observer.
- B. Intra-observer.

I. Normality test:

Exploration of the given data was performed using Shapiro-Wilk test and Kolmogorov-Smirnov test for normality. As Listed in (Table 11) and showed in (Figure 53), it was revealed that the significant level (P-value) was shown to be insignificant as P-value > 0.05 , which indicated that alternative hypothesis was rejected, and the concluded data originated from normal distribution (parametric data) resembling normal Bell curve in pre & post measurements while P value was significant in the difference between both groups which indicated nonparametric data.

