Table (11): Normality exploration of both groups regarding all measurements:

Measurements		Group I Single Coil Spring	Group II Double Coil Spring
Skeletal.	Pre	> 0.05	> 0.05
	Post	> 0.05	> 0.05
	Difference	$< 0.05^*$	$< 0.05^*$
Dental	Pre	> 0.05	> 0.05
	Post	> 0.05	> 0.05
	Difference	$< 0.05^*$	$< 0.05^*$
Soft tissue	Pre	> 0.05	> 0.05
	Post	> 0.05	> 0.05
	Difference	$< 0.05^*$	$< 0.05^*$

* Significant difference as $P < 0.05$

[figure not shown]
[figure not shown]

Figure (53): Scattered chart represents normal bell curve of normality test.

II. Baseline characterized:

1. Age:

In group I, minimum age was (18.4), maximum was (21.2), while mean \pm standard deviation was (19.42 ± 1.03) . In group II, minimum age was (18.08), maximum was (23.17), while mean \pm standard deviation was (20.7 ± 2.24) , as presented in table (12) and figure (54).

Comparison between both groups was performed by using Independent t-test which revealed insignificant difference between them as $P > 0.05$, as presented in table (12).

Table (12): Minimum, maximum, mean & standard deviation of age in both groups:

	Min	Max	M	SD	P value
G I	18.4	21.2	19.42	1.03	0.09
G II	18.08	23.17	20.7	2.24	

N: count

Min: minimum

Max: maximum

M: mean

SD: standard deviation

[figure not shown]

Figure (54): Bar chart showing mean of age in both groups.

2. Gender:

In gender all companions were performed by using Chi square test. In group I, male (16.67%) was significantly lower than female (83.3%) as $P < 0.05$, while in group II male (33.3%) was insignificantly lower than female (66.6%) as $P > 0.05$, as presented in table (13) and figure (55).

Also, comparison between group I & II reveled insignificant difference between them in both male & female as $P > 0.05$ as presented in table (13).

Table (13): Frequency & percentage of gender distribution in both groups:

Group	Male		Female		P value
	N	%	N	%	
Group I	2	16.67%	10	83.33%	0.001*
Group II	3	33.33%	6	66.67%	0.13
P value	0.34		0.34		

N: count

%: percentage

P: probability level which is significant at $P \leq 0.05$

[figure not shown]

Figure (55): Bar chart showing percentage of gender distribution in both groups

3. Duration:

In group I, minimum duration was (5.5 months), maximum was (9.73 months), while mean \pm standard deviation was (8.03 ± 2.9) . In group II, minimum duration was (4 months), maximum was (14.9 months), while mean \pm standard deviation was (10.59 ± 3.89) .

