Comparison between both groups was performed by using Independent t-test which revealed insignificant difference between them as $P>0.05$, as presented in table (14) and figure (56).

Table (14): Minimum, maximum, mean & standard deviation of duration in months in both groups:

	Min	Max	M	SD	P value
Group I	5.50	9.73	8.03	2.90	0.09
Group II	4.00	14.90	10.59	3.89	

M: mean SD: standard deviation

P: probability level which is significant at $P \leq 0.05$

[figure not shown]

Figure (56): Bar chart showing mean of duration in months in both groups.

III. Measurements:

A. Skeletal:

1. Anteroposterior:

- Group I:**

In group I pretreatment records, post treatment records and difference between them regarding anteroposterior skeletal measurements were presented in table (15) and figure (57).

Comparison between pretreatment & post treatment records was performed by using Paired t-test which revealed insignificant difference between them in all measurements as $P > 0.05$, as presented in table (15).

Table (15): Mean & standard deviation of pretreatment, post treatment records and difference between them regarding anteroposterior skeletal measurements in group I:

Group I Anteroposterior Skeletal Measurements	Pre		Post		Difference		P value
	M	SD	M	SD	M	SD	
SNA angle	83.41	4.33	83.47	3.90	0.05	1.26	0.854
SNB angle	77.98	3.18	77.44	2.53	-0.54	1.36	0.194
ANB angle	5.50	2.11	6.07	2.53	0.57	1.72	0.273
A-NV distance	6.79	4.69	6.96	3.87	0.17	1.11	0.611
Pog-NV distance	6.06	6.44	6.02	5.32	-0.04	2.20	0.951

M: mean SD: standard deviation

P: probability level which is significant at $P \leq 0.05$

[figure not shown]

Figure (57): Bar chart showing mean of pretreatment, post treatment records and difference between them regarding anteroposterior skeletal measurements in group I.

- **Group II:**

In group II pretreatment records, post treatment records and difference between them regarding anteroposterior skeletal measurements were presented in table (16) and figure (58).

Comparison between pretreatment & post treatment records was performed by using Paired t-test which revealed insignificant difference between them in all measurements as $P > 0.05$, as presented in table (16).

Table (16): Mean & standard deviation of pretreatment, post treatment records and difference between them regarding anteroposterior skeletal measurements in group II:

Group II Anteroposterior Skeletal Measurements	Pre		Post		Difference		P value
	M	SD	M	SD	M	SD	

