Comparison between pretreatment & post treatment records was performed by using Paired t-test which revealed insignificant difference between them in all measurements as $P > 0.05$ except U1-FHP and U5-FHP (Post was significantly higher than prerecord) as $P < 0.05$, as presented in table (21).

Table (21): Mean & standard deviation of pretreatment, post treatment records and difference between them regarding anteroposterior angular dental measurements in group I:

Group I Anteroposterior Angular Dental Measurements	Pre		Post		Difference		P value
	M	SD	M	SD	MD	SD	
U1-NA	25.83	9.57	26.27	10.17	0.44	1.88	0.437
U1-FHP	123.54	12.59	124.50	12.88	0.97	1.46	0.042*
U4-FHP	102.14	9.64	103.24	11.70	1.10	4.80	0.444
U5-FHP	96.83	11.01	101.88	13.25	5.06	6.02	0.014*
U6-FHP	94.43	8.90	89.70	9.02	-4.72	9.69	0.119
U7-FHP	87.70	10.16	82.83	8.09	-4.87	8.16	0.063

M: mean

SD: standard deviation

MD: mean difference

P: probability level which is significant at $P \leq 0.05$

[figure not shown]

Figure (63): Bar chart showing mean of pretreatment, post treatment records and difference between them regarding anteroposterior angular dental measurements in group I.

- **Group II:**

In group II pretreatment records, post treatment records and difference between them regarding anteroposterior- angular- dental measurements were presented in table (22) and figure (64).

Comparison between pretreatment & post treatment records was performed by using Paired t-test which revealed insignificant difference between them in all measurements as $P > 0.05$ except U4-FHP and U5-FHP (Post records were significantly higher than prerecords), and U6-FHP (Post record was significantly lower than prerecord) as $P < 0.05$, as presented in table (22).

Table (22): Mean & standard deviation of pretreatment, post treatment records and difference between them regarding anteroposterior angular dental measurements in group II:

Group II Anteroposterior Angular Dental Measurements	pre		post		Difference		P value
	M	SD	M	SD	MD	SD	
U1-NA	16.88	4.94	17.05	5.79	0.18	0.85	0.67
U1-FHP	114.61	4.00	115.05	4.83	0.43	0.83	0.44
U4-FHP	105.26	5.30	109.68	4.81	4.42	5.18	0.034*
U5-FHP	102.27	4.80	108.52	5.79	6.25	5.34	0.008*
U6-FHP	97.77	1.80	84.23	9.21	-13.54	8.61	0.002*
U7-FHP	88.47	8.81	80.17	9.62	-8.30	0.81	0.077

M: mean

SD: standard deviation

MD: mean difference

P: probability level which is significant at $P \leq 0.05$

[figure not shown]

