In group I pretreatment records, post treatment records and difference between them regarding crown inclination- angular- dental measurements were presented in table (27) and figure (69).

Comparison between pretreatment & post treatment records was performed by using Paired t-test which revealed insignificant difference between them in all measurements as $P > 0.05$ except U4 and U5 as there was a statistically significant difference as $P < 0.05$ (Post was significantly higher than prerecord), as presented in table (27).

Table (27): Mean & standard deviation of pretreatment, post treatment records and difference between them regarding crown inclination - angular dental measurements in group I:

Group I Crown Inclination Angular Dental Measurements	Pre		Post		Difference		P value
	M	SD	M	SD	MD	SD	
U4	4.80	2.34	11.94	7.12	7.14	7.61	0.008*
U5	6.47	4.23	13.79	7.28	7.32	6.86	0.004*
U6	4.84	4.06	4.81	2.95	-0.03	3.87	0.980
U7	5.76	3.65	7.94	7.83	2.19	5.81	0.219

M: mean

SD: standard deviation

MD: mean difference

P: probability level which is significant at $P \leq 0.05$

[figure not shown]

Figure (69): Bar chart showing mean of pretreatment, post treatment records and difference between them regarding crown inclination - angular dental measurements in group I.

- **Group II:**

In group II pretreatment records, post treatment records and difference between them regarding crown inclination- angular- dental measurements were presented in table (28) and figure (70).

Comparison between pretreatment & post treatment records was performed by using Paired t-test which revealed significant difference between them in all measurements as $P < 0.05$ except U5 as there was a statistical insignificant difference as $P > 0.05$ (Post was significantly higher than prerecord), as presented in table (28).

Table (28): Mean & standard deviation of pretreatment, post treatment records and difference between them regarding crown inclination - angular dental measurements in group II:

Group II Crown Inclination Angular Dental Measurements	pre		post		Difference		P value
	M	SD	M	SD	MD	SD	
U4	5.11	3.82	12.77	6.01	7.66	7.31	0.014*
U5	8.28	5.27	14.25	7.50	5.98	8.45	0.067
U6	2.99	1.67	7.12	4.47	4.13	3.66	0.010*
U7	5.23	4.77	9.23	6.85	3.99	5.11	0.047*

M: mean SD: standard deviation

MD: mean difference

P: probability level which is significant at $P \leq 0.05$

Crown inclination / Angular Dental Measurements Group II

[figure not shown]

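### Group I treatment duration (SAP Table 14) has an SD of 2.90 months that its own range of 5.50 to 9.73 cannot produce, and duration is filed as a baseline characteristic

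*SAP*

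**What the plan says.** The SAP, under II.3 Duration, reports for Group I that "minimum duration was (5.5 months), maximum was (9.73 months", with mean 8.03 and SD 2.9. Table 14 carries the same row: "Group I 5.50 9.73 8.03 2.90 0.09" (minimum, maximum, mean, SD, P). Group II is given as 4.00, 14.90, 10.59 and 3.89. The stated conclusion is an "Independent t-test which revealed insignificant difference between them as $P>0.05".

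The list of tests covers this comparison in one line: "Comparison between quantitative continuous data (Age & Duration) was performed by Independent t-test". It does not say whether the test is pooled or Welch, and Table 14 prints no n. In the results outline, duration is item C under "II. Baseline characteristics".

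The protocol (Procedure) has a levelling phase first, then reactivation visits every four weeks until a Class I molar relationship is judged clinically to be reached. Under Methods of assessment it says that the rate of tooth movement will be analysed on digital models taken every four weeks.

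**The concern.** An SD is limited by the range of the data. The Group I range is only 4.23 months, and an SD of 2.90 is too large for it. The text and the table agree, so this is not a table damaged in PDF extraction. At least one printed figure is wrong, and a between-arm conclusion rests on the same row.

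The heading matters too. In a trial that treats until a clinical endpoint is met, a duration in months reads as time under treatment, which is observed after allocation. Filed as baseline, a difference of 2.56 months between arms looks like a balance check when it may be a treatment result. The SAP does not define duration, so this reading is an inference, though a strong one.

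A separate point does not add to the seriousness of the first. The supplied SAP has no analysis of rate of movement. It reports displacement and duration by arm, but not the per-patient rate that the protocol planned.

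**Working it through.** **Inputs.** Group I duration: min 5.50, max 9.73, mean 8.03, SD 2.90. Group II: mean 10.59, SD 3.89 (SAP Table 14). Group sizes come from Table 13: Group I row "Group I 2 16.67% 10 83.33% 0.001", so 2 + 10 = 12; Group II, 3 + 6 = 9. All tests are taken as two-sided.

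**Check on n.** A one-sample t on the differences, t = MD/(SD/√n), gives:
- Table 21 row "U5-FHP 96.83 11.01 101.88 13.25 5.06 6.02 0.014": P = 0.0192 at n = 11, 0.0141 at 12, 0.0105 at 13 (printed 0.014).
- Table 28 row "U5 8.28 5.27 14.25 7.50 5.98 8.45 0.067": P = 0.0854 at n = 8, 0.0665 at 9, 0.0520 at 10 (printed 0.067).

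Allowing for rounding of the inputs, all six rows of Table 21 fit n = 12 and none fits 11 or 13. All four rows of Table 28 fit n = 9 and none fits 8 or 10.

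**Largest possible SD, any mean.** The range is 9.73 − 5.50 = 4.23.
- n = 12, half the values at each limit: (4.23/2) × √(12/11) = 2.21.
- n = 3 or 4, the most generous case for any n of 3 or more: 4.23/√3 = 2.44.
- n = 2 could give about 2.99, but the mean would then be (5.50 + 9.73)/2 = 7.615, not 8.03.

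**Attainable SD with mean 8.03 and n = 12.**
- Largest: four values at 5.50, seven at 9.73 and one at 6.25. Squared deviations sum to 49.00, and √(49.00/11) = 2.11 (2.12 if the inputs sit at their rounding limits).
- Smallest: one value at each limit and ten equal values at (96.36 − 15.23)/10 = 8.113, which gives 0.92.

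The printed 2.90 is outside 0.92 to 2.11. Group II passes the same check (3.89, attainable 2.80 to 5.32).

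**If the SD and mean are right instead,** and only one limit is wrong, the maximum must be about 11.3 or more, or the minimum about 3.2 or less.

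**Effect on the test.** Mean difference 10.59 − 8.03 = 2.56 months, n = 12 and 9. First the SAP's own figure, with the printed SDs: pooled SD = √[(11 × 2.90² + 8 × 3.89²)/19] = 3.353; SE = 3.353 × √(1/12 + 1/9) = 1.478; t = 2.56/1.478 = 1.73; P = 0.0995. The printed 0.09 follows only by truncation, since 0.0995 rounds to 0.10.

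| Group I SD | Pooled P (95% CI, months) | Welch P (95% CI, months) |
|---|---|---|
| 0.92 | 0.039 (0.14 to 4.98) | 0.086 (−0.45 to 5.57) |
| 2.11 | 0.067 (−0.20 to 5.32) | 0.100 (−0.58 to 5.70) |
| 2.90 (as printed) | 0.0995 (−0.53 to 5.65) | 0.119 (−0.74 to 5.86) |

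Pooled df is 19; Welch df is 8.7, 11.5 and 14.3. P reaches 0.05 or below only with the pooled test and a Group I SD of about 1.51 or less.

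**The case against.** The strongest reply is that the documents hint at where the error lies. Age and duration share one line in the list of tests. For age, Table 12 prints P = 0.09; with n = 12 and 9 the pooled test gives 0.095 and Welch 0.141, so the age test looks pooled. On a pooled reading, duration with SD 2.90 gives 0.0995, close to the printed 0.09, whereas no attainable SD gives more than 0.067. That fits a test run with SD 2.90 and a misprinted range limit, in which case the conclusion of no significant difference would stand. This is plausible but does not settle the matter: 0.0995 rounds to 0.10, and Welch with an attainable SD also gives about 0.09.

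Four smaller objections are fair in part:
- The check on n uses two tables, and some paired rows elsewhere do not reproduce at the Table 13 sizes. For example, Table 36 U4 is printed as 0.438, but its MD and SD give about 0.001 at n = 12. Table 13 is enough for n by itself.
- The protocol does state when distalization counts as achieved. What is missing is a definition of duration in the SAP, above all its start.
- The supplied SAP is an extract: it cites 43 tables and shows Tables 11 to 41. A rate analysis elsewhere cannot be excluded.
- Neither document names duration as a primary outcome, so the error touches one secondary comparison.

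None of these makes the printed row possible.

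**Conclusion.** The concern holds. The Group I duration row is arithmetically impossible: an SD of 2.90 against a ceiling of 2.11 with the stated mean and n = 12, or 2.44 with any mean and any n of 3 or more. The impossibility does not depend on the Table 13 sample size. The P values and intervals do, and they also assume that the Group II figures and both means are correct.

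The stated absence of a difference is unverified, not refuted. Across the readings considered, P runs from 0.039 to 0.119, and it falls to 0.05 or below only if the test was pooled and the true SD is about 1.51 or less; the printed P would then be wrong as well. All the intervals are wide, with upper limits of about 5 to 6 months.

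Filing duration as baseline is a labelling fault that changes no number but does change how the difference is read. The missing rate analysis is a separate omission, claimed only for the supplied text. This should be fixed; it does not overturn the trial's main comparisons.

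**What to change.** 1. Check the Group I minimum, maximum, mean and SD against patient-level data, and correct Table 14 and the text.
2. Rerun the comparison. Give n per group, say whether the test is pooled or Welch, and report the mean difference with its 95% CI.
3. Move duration out of the baseline section, report it as a post-allocation outcome, and define its start and end, including whether levelling counts.
4. Separately, report a per-patient rate in mm/month from the four-weekly models, compared between arms with a 95% CI, or state that this analysis was dropped and why.

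Items 1 to 3 cost little: a source-data check, one recomputed test and a changed heading with a definition. Item 4 costs measuring time if the four-weekly models were taken, which the SAP does not show, or one sentence if the analysis was dropped.

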Figure (70): Bar chart showing mean of pretreatment, post treatment records and difference between them regarding crown inclination - angular dental measurements in group II.

- **Comparison between both groups:**

Comparison between group I & II regarding difference between pretreatment & posttreatment records of crown inclination - angular dental measurements was performed by using Mann Whitney test which revealed insignificant difference between them regarding all measurements except U6 (Group I was significantly lower than group II) as $P < 0.05$, as presented in table (29) and figure (71).

Table (29): Comparison between both groups regarding crown inclination - angular dental measurements:

Difference Crown Inclination Angular Dental Measurements	Group I		Group II		P value
	MD	SD	MD	SD	
U4	7.14	7.61	7.66	7.31	0.86
U5	7.32	6.86	5.98	8.45	0.71
U6	-0.03	3.87	4.13	3.66	0.04*
U7	2.19	5.81	3.99	5.11	0.27

SD: standard deviation

MD: mean difference

P: probability level which is significant at $P \leq 0.05$

[figure not shown]

Figure (71): Bar chart showing comparison between both groups regarding crown inclination - angular dental measurement.

2. Linear

a. Anteroposterior

- Group I:**

In group I pretreatment records, post treatment records and difference between them regarding anteroposterior- linear- dental measurements were presented in table (30) and figure (72). Comparison between pretreatment & post treatment records was performed by using Paired t-test which revealed insignificant difference between them in all measurements as $P > 0.05$ except U4-apex/S Ver and U5-apex/S Ver (Post was significantly higher than prerecord), MBc6/S Ver (Post was significantly lower than prerecord), as there was a statistical significant difference as $P < 0.05$, while in U5-tip/S Ver (Post was higher than pre), U6-apex/S Ver, MBc7/S Ver and U7-apex/S Ver (post was lower than pre) there was a highly statistical significant difference as $P < 0.0001$, as presented in table (30).

Table (30): Mean & standard deviation of pretreatment, post treatment records and difference between them regarding anteroposterior - linear dental measurements in group I:

Group I Anteroposterior Linear Dental Measurements	Pre		Post		Difference		P value
	M	SD	M	SD	MD	SD	
U1-tip/S Ver	78.77	6.89	78.79	7.17	0.02	0.47	78.77
U1-apex/S Ver	66.06	3.55	66.04	3.69	-0.02	1.21	0.861
L1-tip/S Ver	72.47	3.99	71.31	4.58	-1.16	2.50	0.948
U4-tip/S Ver	61.06	3.77	62.11	3.94	1.06	1.17	0.124

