U4-apex/S Ver	57.08	3.56	59.67	3.11	2.59	1.64	0.010*
U5-tip/S Ver	54.68	3.61	56.08	3.71	1.40	1.00	0.000**
U5-apex/S Ver	52.57	2.51	54.42	2.71	1.86	1.55	0.001*
MBc6/S Ver	48.60	3.53	44.82	3.35	-3.78	1.31	0.002*
U6-apex/S Ver	47.70	3.06	44.92	2.83	-2.78	1.64	0.000**
MBc7/S Ver	37.47	3.57	34.21	3.32	-3.26	1.55	0.000**
U7-apex/S Ver	37.79	2.65	35.29	3.44	-2.50	2.45	0.000**
overjet	6.30	3.52	7.48	5.46	1.19	2.43	0.311

M: mean

SD: standard deviation

MD: mean difference

P: probability level which is significant at $P \leq 0.05$

[figure not shown]

Figure (72): Bar chart showing mean of pretreatment, post treatment records and difference between them regarding anteroposterior - linear dental measurements in group I.

- **Group II:**

In group II pretreatment records, post treatment records and difference between them regarding anteroposterior- linear- dental measurements were presented in table (31) and figure (73).

Comparison between pretreatment & post treatment records was performed by using Paired t-test which revealed insignificant difference between them in all measurements as $P > 0.05$ except U4-apex/S Ver U5-tip/S Ver, U5-apex/S Ver (Post was significantly higher than prerecord and MBc6/S Ver , U6-apex/S Ver , MBc7/S Ver & U7-apex/S Ver (Post was significantly lower than prerecord), as there was a statistical significant difference as $P < 0.05$, , as presented in table (31).

Table (31): Mean & standard deviation of pretreatment, post treatment records and difference between them regarding anteroposterior - linear dental measurements in group II:

Group II Anteroposterior Linear Dental Measurements	pre		post		Difference		P value
	M	SD	M	SD	MD	SD	
U1-tip/S Ver	76.89	2.86	77.48	2.99	0.59	0.13	0.12
U1-apex/ S Ver	67.13	3.09	67.56	3.18	0.43	0.08	0.25
L1-tip/S Ver	72.48	3.32	71.93	4.20	-0.54	1.61	0.342
U4-tip/S Ver	63.21	3.81	64.32	4.43	1.11	1.76	0.095
U4-apex/S Ver	57.90	3.53	59.69	2.68	1.79	1.19	0.002*
U5-tip/S Ver	56.43	3.58	58.31	3.87	1.88	1.49	0.005*
U5-apex/S Ver	53.48	2.83	54.85	2.27	1.37	1.58	0.031*
MBc6/S Ver	50.55	3.53	46.04	5.61	-4.51	3.39	0.004*
U6-apex/S Ver	48.06	3.97	45.94	5.17	-2.12	2.52	0.035*
MBc7/S Ver	39.93	3.98	34.61	5.39	-5.32	3.62	0.002*
U7-apex/S Ver	39.18	3.01	36.79	2.75	-2.40	0.98	0.000**
overjet	4.46	1.63	5.31	1.99	0.85	1.25	0.074

M: mean

SD: standard deviation

MD: mean difference

P: probability level which is significant at $P \leq 0.05$

[figure not shown]

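### In three of four premolar rows the mean angle to FHP rises while the mean tip-minus-apex distance falls, so the direction of premolar tipping is unreconciled

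*SAP*

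**What the plan says.** The SAP measures each upper premolar in the sagittal direction in two ways.

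**Angle to FHP.** Table 21 (Group I) reports no significant change "except U1-FHP and U5-FHP (Post was significantly higher than prerecord". The U4 row is not significant: "U4-FHP 102.14 9.64 103.24 11.70 1.10 4.80 0.444". Table 22 (Group II) reports no significant change "except U4-FHP and U5-FHP (Post records were significantly higher than prerecords), and U6-FHP (Post record was significantly lower than prerecord".

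**Tip and apex distance to S Ver.** The Table 30 text (Group I) lists as exceptions "except U4-apex/S Ver and U5-apex/S Ver (Post was significantly higher than prerecord", with U5-tip also raised. The Table 31 text (Group II) reads "except U4-apex/S Ver U5-tip/S Ver, U5-apex/S Ver (Post was significantly higher than prerecord". All four premolar rows move forward at both tip and apex.

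The text says only that post values exceed pre values. It does not compare the two sets of tables, does not say that premolars tipped, and does not define FHP, S Ver, the tip or apex landmarks, or the angle convention.

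**The concern.** The angle and the two positions describe the same teeth. If a larger angle means that the crown lies further ahead of the root, a rising angle needs a rising tip-minus-apex distance. Three premolar rows show the reverse.

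The Protocol uses mini screws as indirect anchorage, and its background treats mesial movement and tipping of premolars as anchorage loss. A reader of Tables 21 and 22 would infer forward crown tipping. A reader of Tables 30 and 31 would infer, for three of the four rows, that the root came forward more than the crown. Significant results stand on both sides: U5-FHP and U5-apex in Group I, U4-FHP and U4-apex in Group II. Whether the premolars tipped or moved bodily cannot be stated until the tables agree.

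**Working it through.** **Inputs.** Group sizes come from the gender table (Table 13): 2+10=12 in Group I and 3+6=9 in Group II. Means, mean differences and SDs come from Tables 21, 22, 30 and 31. Tooth length L is not given; I assume 15 to 22 mm.

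**1. Reproduce the printed angle results.** Two-sided paired t = MD/(SD/√n):
- Group I U4: 1.10/(4.80/√12)=0.79, P=0.444 (printed 0.444)
- Group I U5: 5.06/(6.02/√12)=2.91, P=0.014 (0.014)
- Group II U4: 4.42/(5.18/√9)=2.56, P=0.034 (0.034)
- Group II U5: 6.25/(5.34/√9)=3.51, P=0.008 (0.008)

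Group II U4-tip (0.095) and U4-apex (0.002) also reproduce at n=9.

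**2. Sign convention.** Assume tip − apex = L·sin(angle − 90). The incisor serves as a check, with L = (tip − apex)/sin(angle − 90):
- Group I: (78.77−66.06)/sin 33.54° = 12.71/0.5525 = 23.0 mm before, 22.5 mm after
- Group II: 9.76/sin 24.61° = 23.4 mm before, 23.4 mm after

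For U6 and U7 in both groups the angle falls and the cusp moves back more than the apex. In Group II U6, for example, the angle changes by −13.54, the cusp by −4.51 and the apex by −2.12. A higher angle therefore goes with a crown further forward of its apex.

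**3. Premolars.**

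| Row | Angle change (degrees) | Tip − apex, pre to post (mm) | Change (mm) | Implied L, pre to post (mm) |
|---|---|---|---|---|
| Group I U4 | +1.10 | 61.06−57.08=3.98 to 62.11−59.67=2.44 | −1.54 | 18.9 to 10.7 |
| Group I U5 | +5.06 | 54.68−52.57=2.11 to 56.08−54.42=1.66 | −0.45 | 17.7 to 8.1 |
| Group II U4 | +4.42 | 63.21−57.90=5.31 to 64.32−59.69=4.63 | −0.68 | 20.2 to 13.7 |
| Group II U5 | +6.25 | 56.43−53.48=2.95 to 58.31−54.85=3.46 | +0.51 | 13.9 to 10.9 |

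The first three rows conflict in sign. The fourth does not.

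**4. Size.** Expected change = L·[sin(post−90) − sin(pre−90)] for L=15 to 22 mm; gap = expected minus printed:
- Group I U4: +0.28 to +0.41 against −1.54; gap 1.82 to 1.95 mm
- Group I U5: +1.30 to +1.91 against −0.45; gap 1.75 to 2.36 mm
- Group II U4: +1.10 to +1.62 against −0.68; gap 1.78 to 2.30 mm

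Read the other way, the positions imply angle changes of −6.0 to −4.1, −1.7 to −1.2 and −2.8 to −1.8 degrees. For Group II U5 they imply +1.3 to +2.0 against the printed +6.25, a difference of size only.

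**5. Other movements.** Rotation in the three rows is +3.06, −5.48 and +0.76 degrees (Tables 24 and 25). A cusp 4 mm off axis (assumed) moves at most 4·sin 5.48° = 0.38 mm. A fixed offset of −10 to +10 degrees between the reference planes still leaves an expected increase in all three rows.

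**6. Table 30 P column.** The U1-tip cell holds 78.77, its own pre-treatment mean. U4-tip prints 0.124, but 1.06/(1.17/√12)=3.14 gives 0.009, while the row below prints 0.010. The upper part of the column is displaced. Steps 2 to 4 use means only and are unaffected.

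**The case against.** The strongest objection is that the conflict rests on an angle convention that the documents never give. The study is titled a three-dimensional assessment, and premolar inclination changed markedly (Tables 27 and 28: U4 4.80 to 11.94 in Group I and 5.11 to 12.77 in Group II; U5 6.47 to 13.79 in Group I). Suppose the FHP angle were a tilt that includes inclination, so that tan²(sagittal) = tan²(tilt) − tan²(inclination), applied to means with tilt = angle − 90:
- Group I U4: sagittal tilt falls from 11.2 to 5.9 degrees, a change of −5.3. That lies inside the position-implied range, so this conflict disappears.
- Group II U4: the rise shrinks from 4.42 to about 1.0 degree, but the sign conflict remains.
- Group I U5: there is no solution, because post-treatment inclination (13.79) exceeds tilt (101.88−90=11.88).

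This reading does not clear the tables, and printed angles above 90 degrees do not fit an unsigned line-to-plane angle. What stands is that a convention or landmark difference could explain part of the conflict. The incisor check cannot rule this out, because U1 has no inclination row. The molar levels are also imperfect: in Group II, U7 before treatment (88.47 degrees) and U6 after (84.23 degrees) have the cusp 0.75 and 0.10 mm ahead of the apex. Only the molar changes support the convention.

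A second objection is that the tip-minus-apex change is not clearly significant. With an assumed tip-apex correlation of 0 to 0.9, P runs from 0.41 to 0.07 for Group I U5 and from 0.37 to 0.046 for Group II U4. Group I U4 gives 0.023 or less, but its angle change has P=0.444. No row clearly has both quantities significant. That limits any claim about true tipping. It does not explain the mismatch: under the stated geometry, variation between patients would move both readings together.

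A reader might infer that the SAP asserts mesial crown tipping in one place and denies it in another, that all premolar results are contradictory, or that the U6-FHP between-group result (P=0.03) falls with them. The documents support none of these. The text never states tipping, Group II U5 agrees in direction, and U6-FHP agrees in sign with its positions.

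**Conclusion.** The point holds for three rows: Group I U4, Group I U5 and Group II U4. Mean angle and mean tip-minus-apex change in opposite directions, with a gap of 1.75 to 2.36 mm at L=15 to 22 mm. The printed forward movements of these tips and apices are 1.06 to 2.59 mm.

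It rests on a sagittal angle taken along the tip-apex line, reference planes that are stable between scans, and one tip and one apex landmark per tooth. The tables partly support these assumptions, but the documents do not state them. The means cannot show which set of tables is wrong, and a convention or landmark difference may account for part of the gap. The Table 30 P values should not be relied on in any case. This should be fixed; confidence is medium.

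**What to change.** - State one angle convention, define FHP and S Ver, and name one tip and one apex landmark per tooth.
- From the stored CBCT landmarks, recompute U4 and U5 angle, tip and apex for every patient.
- Check per patient that the FHP angle change and the change in tip minus apex have the same sign. Correct whichever of Tables 21–23 or 30–32 is wrong, and realign the Table 30 P column.
- Until this is done, draw no tipping-versus-bodily conclusion for the premolars. Flag U5-FHP and U5-apex in Group I, and U4-FHP and U4-apex in Group II, as unreconciled.
- The Group II U5 and U6-FHP results need not be withdrawn on this ground.

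The cost is some re-measurement and table correction, with no new scans or patients. Some significant results may change.
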